12.2 Subject demographics and other baseline characteristics

Demographics and other baseline data (including disease characteristics) will be listed and summarized descriptively by treatment arm for the FAS.

Relevant medical histories and current medical conditions at baseline will be summarized separately by system organ class and preferred term by treatment arm.

12.3 Treatments

The Safety set will be used for the analyses below.

The duration of exposure in weeks of capmatinib and pembrolizumab, as well as the dose intensity (computed as the ratio of actual cumulative dose received and actual duration of exposure) and the relative dose intensity (computed as the ratio of dose intensity and planned dose intensity) will be summarized by means of descriptive statistics using the safety set.

The duration of exposure will also be presented for each study drug.

The number of subjects with dose adjustments (reductions, interruption, or permanent discontinuation) and the reasons will be summarized by treatment arm and all dosing data will be listed.

Concomitant medications and significant non-drug therapies prior to and after the start of the study treatment will be listed by subject and summarized by anatomical therapeutic chemical classification system (ATC) term and treatment arm.

12.4 Analysis of the primary endpoint(s)

12.4.1 Efficacy endpoints

The primary endpoint of this study is the progression-free survival (PFS). Estimation of PFS will be provided by treatment arm, based on the FAS population.

12.4.1.1 Definition of primary endpoint(s)

PFS is defined as the time from the date of randomization to the date of the first documented progression or death due to any cause. PFS will be assessed via local review according to RECIST v1.1 (see [Section 16.1](#) for further details). Censoring conventions are provided below in [Section 12.4.1.3](#).

12.4.1.2 Statistical hypothesis, model, and method of analysis

Kaplan-Meier curves for PFS as well as estimated median PFS along with their two-sided 95% confidence intervals will be presented for each treatment arm. The FAS will be used.

12.4.1.3 Handling of missing values/censoring/discontinuations

PFS will be censored at the date of the last adequate tumor assessment prior to the earliest of analysis cut-off date, the start of a subsequent anti-neoplastic therapy (if any), the date of sponsor's decision to discontinue capmatinib (applicable only to subjects on the combination arm), or if the event occurred after two or more missing tumor assessments. Clinical progression without objective radiological evidence will not be considered as documented disease progression. Subjects should be followed for documented progression after discontinuation of treatment for such clinical progression. The date of last adequate tumor assessment is the date of the last tumor assessment with overall lesion response of CR, PR or SD before an event or a censoring reason has occurred. If no post-baseline assessments are available (before an event or a censoring reason occurred), the date of treatment randomization will be used.

The number of subjects censored and reasons for censoring will be summarized by treatment arm using descriptive statistics.

More details will be provided in the SAP.

12.4.1.4 Sensitivity and Supportive analyses

To further explore the potential lasting effect of capmatinib, a supportive analysis of PFS will be performed without censoring data before the date of sponsor's decision to discontinue capmatinib. Kaplan-Meier curves for such PFS as well as estimated median PFS along with their two-sided 95% confidence intervals will be presented for each treatment arm.

12.5 Analysis of secondary endpoints

The secondary efficacy endpoints are ORR, DCR, TTR, DOR as per RECIST 1.1 and OS.

Estimation of all the secondary endpoints will be provided by treatment arms based on the FAS. All relative listings, tables and figures will be presented by treatment arm, unless otherwise specified.

ORR and DCR will be summarized along with their accompanying 95% confidence interval. TTR, DOR and OS will be summarized using the Kaplan-Meier estimators for the medians along with their accompanying 95% confidence intervals. Kaplan-Meier curves will also be provided.

Individual lesion measurements, overall response assessments per RECIST 1.1 as well as BOR will be listed by subject and assessment date.

12.5.2 Safety endpoints

For all safety analyses, the safety set will be used. All listings and tables will be presented by treatment arm.

The overall observation period will be divided into three mutually exclusive segments:

Pre-treatment period:

- from day of subject's first informed consent to the day before first administration of study treatment

On-treatment period:

- Single agent arm: from date of first administration of study treatment to 30 days after date of last actual administration of any study treatment (including start and stop date).
- Combination arm: from date of first administration of any study drug to 30 days after date of last actual administration of any study drug (including start and stop date).

Post-treatment period:

- Single agent arm: starting at day 31 after last administration of study treatment.
- Combination arm: starting at day 31 after the last administration of study treatment.

Safety summaries (tables, figures) include only data from the on-treatment period with the exception of baseline data which will also be summarized where appropriate (e.g. change from baseline summaries). In addition, a separate summary for death including on treatment and post treatment deaths will be provided. In particular, summary tables for adverse events (AEs) will summarize only on-treatment events, with a start date during the on-treatment period (treatment-emergent AEs).

The on-treatment period lasts from the date of first administration of study treatment to 30 days after the date of the last actual administration of any study treatment.

Adverse events

All information obtained on adverse events will be displayed by treatment arm and subject. Summary tables for adverse events (AEs) will include only AEs that started or worsened during the on-treatment period, the **treatment-emergent** AEs. The incidence of treatment-emergent adverse events (new or worsening from baseline) will be summarized by system organ class and or preferred term, severity (based on CTCAE grades), type of adverse event, relation to study treatment. Serious adverse events and non-serious adverse events during the on-treatment period will be tabulated. All deaths (on-treatment and post-treatment) will be summarized.

All AEs, deaths, and serious adverse events (including those from the pre and post-treatment periods) will be listed and those collected during the pre-treatment and post-treatment period will be flagged.

Vital signs

The following will be reported:

- Summary of notable vital sign values

Table with descriptive statistics at baseline, one or several post-baseline time points and change from baseline to this/these post-baseline time points

12-lead ECG

- 12-lead ECGs including PR, QRS, QT, QTcF intervals and heart rate (HR) will be obtained for each subject during the study. ECG data will be read and interpreted locally.
- A listing of these subjects will be produced (by treatment arm).

Clinical laboratory evaluations

All laboratory data will be listed by treatment arm, subject, and visit/time and if normal ranges are available abnormalities will be flagged. Summary statistics will be provided by treatment and visit/time. Shift tables using the low/normal/high/ (low and high) classification will be used to compare baseline to the worst on-treatment value.

Grading of laboratory values will be assigned programmatically as per NCI Common Terminology Criteria for Adverse Events (CTCAE) version 5.0. The calculation of CTCAE grades will be based on the observed laboratory values only, clinical assessments will not be taken into account.

CTCAE Grade 0 will be assigned for all non-missing values not graded as 1 or higher. Grade 5 will not be used.

For laboratory tests where grades are not defined by CTCAE v5.0, results will be categorized as low/normal/high based on laboratory normal ranges.

The following summaries will be generated separately for hematology, and biochemistry tests:

- Listing of all laboratory data with values flagged to show the corresponding CTCAE v5.0 grades if applicable and the classifications relative to the laboratory normal ranges

For laboratory tests where grades are defined by CTCAE v5.0

- Worst post-baseline CTCAE grade (regardless of the baseline status). Each subject will be counted only once for the worst grade observed post-baseline.
- Shift tables using CTCAE v5.0 grades to compare baseline to the worst on-treatment value

For laboratory tests where grades are not defined by CTCAE v5.0,

- Shift tables using the low/normal/high/ (low and high) classification to compare baseline to the worst on-treatment value.

In addition to the above-mentioned tables and listings, other exploratory analyses, for example, figures plotting time course of raw or change in laboratory tests over time or box plots might be specified in the SAP.

Other safety evaluations

Any other safety information collected will be listed and notable values will be flagged. Any statistical tests performed to explore the data will be used only to highlight any interesting comparisons that may warrant further consideration.

Immunogenicity

Immunogenicity will be characterized descriptively by tabulating anti-drug antibodies (ADA) prevalence at baseline and ADA incidence on-treatment. The impact of immunogenicity on PK, safety, and efficacy will be explored. Further details will be specified in the SAP.

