2.1.1 General definitions

2.1.1.1 Study drug and study treatment

Investigational drug will refer to either INC280 or PEMBRO. The terms investigational drug and study drug are used interchangeably. Study treatment refers to both INC280 + PEMBRO and PEMBRO alone.

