2.1.1.2 Date of first/last administration of study treatment

For PEMBRO single agent treatment, the date of first (last) administration of study treatment is derived as the first (last) date when a non-zero dose of PEMBRO was administered and recorded on the DAR eCRF.

For INC280 + PEMBRO, the date of first (last) administration of study treatment is derived as the first (last) date when a non-zero dose of any component of study treatment was administered and recorded on the DAR eCRF.

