2.1.1.5 On-treatment assessment/event and observation periods

For all safety reporting the overall observation period will be divided into three mutually exclusive segments:

- **pre-treatment period:** from day of subject's informed consent to the day before first administration of study treatment
- **on-treatment period:** from date of first administration of study treatment to 30 days after date of last administration of study treatment (including start and stop dates)
- **post-treatment period:** starting at Day 31 after last administration of study treatment.

If dates are incomplete in a way that clear assignment to pre-, on-, post-treatment period cannot be made, then the respective data will be assigned to the on-treatment period.

Safety summaries (tables, figures) include only data from the on-treatment period with the exception of baseline data which will also be summarized where appropriate (e.g., change from baseline summaries). In addition, a separate summary for death including on-treatment and post-treatment deaths will be provided. In particular, summary tables for AEs will summarize only on-treatment events, with a start date during the on-treatment period (treatment-emergent AEs).

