2.8.1 Adverse events (AEs)

AE summaries will include all AEs occurring during on-treatment period. All AEs collected in the AE eCRF page will be listed along with the information collected on those AEs, (e.g., AE relationship to study drug, AE outcome, etc.). AEs starting during the post-treatment period will be flagged in the listings.

AEs will be summarized by number and percentage of subjects having at least one AE in each primary SOC and for each PT using MedDRA coding. A subject with multiple occurrences of an AE will be counted only once in the respective AE category. A subject with multiple CTCAE grades for the same PT will be summarized under the maximum CTCAE grade recorded for the event. AE with missing CTCAE grade will be included in the 'All grades' column of the summary tables.

In AE summaries by primary SOC and PT, the primary SOC will be presented alphabetically and the PT will be sorted within primary SOC in descending frequency. Tables by either primary SOC or PT will be sorted in descending frequency.

The following AE summaries will be produced for all subjects:

- Overview of AEs summarized by relationship and deaths (number and % of subjects who died, with any AE, any SAE, fatal SAEs, AEs leading to dose reduction/interruptions, AE leading to treatment discontinuation, AEs requiring concomitant or additional treatment);
- AEs by SOC and PT, summarized by relationship (all AEs and AEs related to study treatment);
- SAEs summarized by relationship (all SAEs and SAEs related to study treatment) and severity;
- AEs leading to treatment discontinuation (all AEs and AEs related to study treatment);

- AEs leading to study treatment dose reduction/interruption (all AEs and AEs related to study treatment);
- AEs requiring concomitant or additional treatment (all AEs and AEs related to study treatment);
- SAEs leading to fatal outcome (all SAEs and SAEs related to study treatment).

The following listings will be produced:

- All AEs (Safety set)
- AEs among subjects who were not treated (screening failure subjects)

The following summaries will be produced for all AEs observed (starting or worsening) during the on-treatment and/or post-treatment periods:

- AEs related to study treatment by SOC and PT;
- SAEs related to study treatment by SOC and PT

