2.8.4 Adverse events of special interest / grouping of AEs

An AESI is a grouping of AEs that are of scientific and medical concern specific to compound INC280. These groupings are defined using MedDRA terms, SMQs (standardized MedDRA queries), HLGs (high level group terms), HLTs (high level terms) and PTs (preferred terms).

Customized SMQs (Novartis MedDRA queries, NMQ) may also be used. A NMQ is a customized group of search terms which defines a medical concept for which there is no official SMQ available or the available SMQ does not completely fit the need. It may include a combination of single terms and/or an existing SMQ, narrow or broad. Pre-defined AESIs for the current study are as follows:

- Hepatotoxicity
- Central nervous system (CNS) toxicity
- Interstitial Lung Disease and Pneumonitis
- QTc interval prolongation
- Pancreatitis
- Drug-drug interactions with strong CYP3A4 inducers
- Teratogenicity
- Renal dysfunction
- Photosensitivity

For each specified AESI, number and percentage of subjects with at least one event of the AESI occurring during on-treatment period will be summarized.

Summaries of these AESIs will be provided by treatment arm (INC280 + PEMBRO and PEMBRO alone). A listing of all grouping levels down to the MedDRA PTs used to define each AESI will be generated.

Note: From the eCRS, only risk where “Core Safety Risk” = Y should be selected to report AESI in the CSR (the variable name in GPS, for “Core Safety Risk”, is “SP”).

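### Combination-arm PFS and BOR are cut when the sponsor stops capmatinib, but no described AE table is, so later pembrolizumab-alone events count under INC280 + PEMBRO

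*Protocol*

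**What the plan says.** **Efficacy.** Protocol 12.4.1.3 and SAP 2.5.3 censor PFS, in the combination arm only, at the last adequate assessment before the sponsor's decision to discontinue capmatinib. Protocol 12.5.1 and SAP 2.7.2 drop later combination-arm assessments from BOR. The Amendment 3 rationale gives the reason: treatment becomes pembrolizumab alone. Uncut PFS and BOR are kept as supportive analyses.

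**Safety window.** Protocol 12.5.2 sets the on-treatment period as "Combination arm: from date of first administration of any study drug to 30 days after date of last actual administration of any study drug". SAP 2.1.1.5 runs it "from date of first administration of study treatment to 30 days after date of last administration of study treatment". For INC280 + PEMBRO, SAP 2.1.1.2 has the first and last administration "derived as the first (last) date when a non-zero dose of any component of study treatment was administered". The last pembrolizumab dose therefore sets the end of the window, however long ago capmatinib stopped. Under Protocol 12.1.3 and SAP 2.2, a subject who received the assigned treatment at least once keeps that arm label.

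**Safety tables.** SAP 2.8.1 states that "AE summaries will include all AEs occurring during on-treatment period". It plans "AEs by SOC and PT, summarized by relationship (all AEs and AEs related to study treatment"), and SAP 2.1.1.1 says "Study treatment refers to both INC280 + PEMBRO and PEMBRO alone". SAP 2.8.4 defines an AESI as a "grouping of AEs that are of scientific and medical concern specific to compound INC280" and adds: "Summaries of these AESIs will be provided by treatment arm (INC280 + PEMBRO and PEMBRO alone").

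**The concern.** The same change in exposure is handled explicitly for efficacy and not at all for safety. Once capmatinib is withdrawn, a combination-arm subject gets the same drug as a control subject, yet that subject's new AEs still count under INC280 + PEMBRO. This includes the AESIs, which were chosen because they are specific to capmatinib. The relationship tables do not separate these events, because relatedness is summarised to the regimen and not to capmatinib.

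This matters more for safety than for efficacy. Under Amendment 03, efficacy results are no longer captured in the eCRF, while AE and SAE capture continues until 30 days after the last dose. One objective is to characterise the safety of capmatinib plus pembrolizumab, and poor tolerability of that combination is why enrolment was halted. A reader of the planned tables could not tell events that arose on the combination from events that arose after capmatinib had been withdrawn.

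**Working it through.** **Inputs**
- Randomised at the halt: 51 combination, 25 pembrolizumab alone (Amendment 3, Study update).
- Ongoing on pembrolizumab alone at 15-Mar-2021, both arms together: 50 (same place).
- Enrolment halt: 21-Jan-2021. No calendar date is given for the sponsor's decision. Capmatinib was stopped immediately after the halt, and its PK sampling ended that day, so 21-Jan-2021 is used here as an assumption.
- No subject treated as of 22-Jan-2020 (Amendment 2, Study update).
- Maximum treatment: 35 cycles of 21 days (Protocol 6.1, 6.1.3), with a ±4-day window for pembrolizumab after the first dose (Protocol 6.7.2).

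**The plan's own figures reproduce.** 51 + 25 = 76 randomised. 35 × 21 = 735 days, and 735 / 30.4375 = 24.1 months, in line with the stated 24 months or so.

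**Subjects affected.** At most 25 of the 50 ongoing subjects can be controls, so at least 50 − 25 = 25 were from the combination arm. 25 / 51 = 49.0%. This lower bound does not depend on the assumed decision date.

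**How far past the stop.** 21-Jan-2021 to 15-Mar-2021 is 53 days. Allowing a 30-day tail for capmatinib, 53 − 30 = 23 days had already passed beyond it.

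**Illustration: a subject dosed on study in all 35 cycles.** From 22-Jan-2020 to 21-Jan-2021 is 365 days, so the part of the AE window up to halt + 30 days is at most 365 + 30 + 1 = 396 days. The whole window and the part after halt + 30 days are then:

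| Dose spacing | AE window (days) | After halt + 30 days | Share |
|---|---|---|---|
| Exactly 21 days | 34 × 21 + 30 + 1 = 745 | at least 745 − 396 = 349 | 46.8% |
| Last dose 4 days early, window anchored to the original schedule | 714 − 4 + 31 = 741 | at least 741 − 396 = 345 | 46.6% |
| Every interval 4 days short, window anchored to the previous dose | 34 × 17 + 31 = 609 | at least 609 − 396 = 213 | 35.0% |

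These are lower bounds for that dosing pattern, because later-randomised subjects had less time before the halt. They are not estimates for the trial. Progression ends study treatment (Protocol 6.1.4.1), and transfer to commercial pembrolizumab is allowed (Protocol 6.1, 9.1.1), so many subjects may leave well before cycle 35.

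**The case against.** The strongest reply is that nothing here is an error. Protocol and SAP agree on the window, it is the same in both arms, and by-arm summaries over it are standard. That stands, and the planned tables should be kept.

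Other points are accurate but do not close the gap:
- SAP 2.4.2 summarises dose reductions, interruptions and discontinuations separately for each component, and SAP 2.4.1.1 derives exposure for each drug. These show how long pembrolizumab outlasts capmatinib, and they bear on tolerability. They are dosing summaries, not AE incidence.
- The AE listing carries relationship to study drug, which SAP 2.1.1.1 defines as either agent. With the dosing listings, a split could be rebuilt afterwards. A split made after results are seen is weaker than one specified now.
- A subject counts once per category, at maximum grade, so not every later event changes a table. A later first occurrence or a worse grade still does, and it can replace the grade recorded during combination treatment.
- The parallel with efficacy is partial. The PFS/BOR cut is in one arm only, and OS is not cut. A different safety window may be deliberate, but the documents give no reason for having no cut version at all.
- A calendar cut still leaves pembrolizumab-only time for subjects who stopped capmatinib earlier because of AEs. This is a real limit of the remedy.
- The TFL shells, a separate document, were not available. If they already contain a split, the SAP needs only to say so.

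**Conclusion.** The concern holds. Among the tables described in the protocol and SAP, none separates AEs on the combination from AEs that start after capmatinib was withdrawn. At least 25 of 51 combination subjects (49%) were still being dosed with pembrolizumab alone 53 days after the halt, taking the halt date as the stop. For a subject treated through all 35 cycles, roughly 35% to 47% or more of the AE window would fall beyond halt + 30 days. That range is illustrative only.

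The number of AEs affected and the effect on the between-arm difference cannot be computed from the documents. The direction is also open: incidence under INC280 + PEMBRO can only rise with the added time, while rates per unit time could be diluted. This is a recommended addition to a valid analysis and does not invalidate the planned tables.

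**What to change.** Keep every any-drug table as planned. In Protocol 12.5.2 and SAP 2.1.1.5 and 2.8:

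1. State the calendar date of the sponsor's decision. The PFS and BOR rules already depend on it.
2. Add supplementary AE, SAE and AESI tables limited, in both arms, to events starting up to that date plus 30 days, or to the end of the subject's on-treatment period if earlier. Show later combination-arm events in a separate column.
3. Describe this as following the reasoning of the PFS/BOR cut without being identical to it. The efficacy cut applies to the combination arm only and has no 30-day tail.
4. Footnote that pembrolizumab-only time in subjects who stopped capmatinib earlier for AEs remains in the cut tables. A subject-level cut would remove it but would make length of follow-up depend on toxicity.

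Exposure-adjusted rates are optional.

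The cost is SAP wording, one period flag from existing AE dates and the decision date, and one extra table set. No new data are needed. Capmatinib effects delayed beyond 30 days would fall in the separate column of the added tables, and they remain in the any-drug tables.
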